**Table 2-1 Visit window**

Protocol defined			Time point to be analyzed	Visit window (days) for mapping end of study visit
Epoch	Week	Day		
Screening	-4	-28 to -1	Baseline	-28 to -1
Open-label treatment	1	1	Baseline	1
	1	3	Day 3	2-4
	2	15	Day 15	5-16
	4	29	Week 4	17-31
	8	57	Week 8	32-60
	12	85	Week 12	61-88
	16	113	Week 16	89-116
	20	141	Week 20	117-144
	24	169	Week 24	145-172
	28	197	Week 28	173-200
	32	225	Week 32	201-228
	36	253	Week 36	229-256
	40	281	Week 40	257-284
	44	309	Week 44	285-312
	48	337	Week 48	313-340
	Every 4 weeks after Week 48	X	Every 4 weeks after Week 48	(X-24) – (X+3)

## 2.2 Analysis sets

The Full Analysis Set (FAS) and Safety set comprise all participants who received at least one dose of study treatment. (See [Section 5.5](#) for the rule of exclusion criteria of analysis sets).

The number of participants who are included in the FAS and the Safety set will be provided.

## **2.2.1 Subgroup of interest**

Adapted ACR30/50/70/90/100 analysis (see primary analysis and secondary analysis), key secondary analysis, and summary of treatment emergent AEs by SOC and PT will be performed by the following subgroups:

- Baseline age (at screening): <65, ≥65 years
- Prior use of Tocilizumab: Yes, No
- Sex: Male, Female
- Weight group: ≤50, >50-≤75, >75 kg

The subgroup based on prior use of Tocilizumab (Yes, No) will be used to perform the additional subgroup analyses for Week 28 IA as follows:

- Adapted ACR 30/50/70/90/100 response by visit
- Oral corticosteroid dose by visit
- Each adapted ACR components by visit
- Rash by visit
- DAS28-CRP by visit
- Systemic feature score: Total score by visit
- Systemic feature score: Each component score by visit
- Number of tender joints
- Number of swollen joints

The subgroup analyses described above based on the subgroup of prior use of Tocilizumab will be performed only for the first 11 participants.

## **2.3 Patient disposition, demographics and other baseline characteristics**

### **2.3.1 Patient disposition**

The number of participants screened, completed screening epoch, and discontinued screening epoch with the reasons for screen failures will be provided.

The number and percentage of participants in the safety set who completed treatment epoch and who discontinued treatment epoch prematurely with the reasons will be presented. At a 28 week analysis or a 48 week analysis, the number and percentage of participants in the safety set who completed Week 28 or Week 48 visit will be presented as completing treatment epoch for the interim analyses.

For each protocol deviation, the number and percentage of participants for whom the deviation applies will be tabulated for the Safety set.

The FPFV and LPLV dates, the number of participants who had IC, treated, discontinued and had AEs related to study treatment will be provided by center at a 28 week analysis for all participants.

### 2.3.2 Demographics and other baseline characteristics

The following common demographic variables will be summarized and listed for the FAS. The threshold used to convert continuous values to categorical variables may change depending on the obtained data.

#### **Continuous variables:**

- Age (years)
- Height (cm)
- Weight (kg)
- Body mass index (BMI)

*Body Mass Index (BMI)* will be calculated when both height and weight are available, using the following formula:

$$\text{BMI} = (\text{body weight in kilograms}) / (\text{height in meters})^2$$

#### **Categorical variables:**

- Age categories (<18, ≥18-<45, ≥45-<65, ≥65)
- Weight categories (≤50, >50-≤75, >75)
- Sex
- Race
- Race as collected
- Ethnicity

The following disease history and baseline characteristics will be summarized for the FAS.

#### **Continuous variables:**

- Body temperature (°C)
- Time from AOSD diagnosis to study entry (screening visit) (years)
- Standardized C-reactive protein (CRP)\*1 (mg/L)
- Oral prednisone equivalent dose at baseline (mg/day)
- Oral prednisone equivalent dose at baseline (mg/kg/day)
- Physician's global assessment of disease activity (VAS) (mm)
- Participant's assessment of disease activity (Participant's overall well-being) (VAS) (mm)
- Participant's assessment of disease activity (Pain) (VAS) (mm)
- Number of active joints (68 joints evaluated for pain/tenderness and 66 for swelling)\*2

- Number of tender joints
- Number of swollen joints
- HAQ functional ability score
- DAS28-CRP
- CCI
- Systemic feature score
- Ferritin (ug/L)

\*1 Standardized C-reactive protein (CRP) (mg/L) will be calculated based on the SI normal range of 0.0-10.0 mg/L using the following formula:

Standardized CRP =  $10 \times [(\text{observed CRP value} - \text{minOMU}) / \text{rangeOMU}]$ ,

where minOMU and rangeOMU are minimum value and range of normal range on the original measurement unit respectively.

\*2 The number of active joints is defined as the number of joints that are tender or swollen.

**Categorical variables:**

- Oral prednisone equivalent dose at baseline (0, >0-≤0.2, >0.2-<0.5, ≥0.5-≤0.8, >0.8 mg/kg/day)
- Rash\* (Yes, No)
- Intermittent fever due to AOSD (Yes, No)
- Prior use of any biologics\*\* (Yes, No)
- Prior use of Tocilizumab (Yes, No)

For the chest X-ray assessment at screening, a listing of participants having a positive result will be listed by participant.

\*Rash is defined by the presence of typical salmon-pink rash on the trunk and elsewhere during the febrile episodes.

\*\*Anakinra, Rilonacept, Tocilizumab, Etanercept, Infliximab, Golimumab, Adalimumab, Abatacept, Rituximab, Certolizumab, and etc.

## **2.4 Treatments (study treatment, rescue medication, concomitant therapies, compliance)**

### **2.4.1 Study treatment / compliance**

The exposure to study drug (number of injections), duration of exposure (days) and total exposure in patient years will be summarized and listed for the Safety set. The number and percentage of participants of certain durations (any exposure, ≥4 weeks (28 days), ≥12 weeks (84 days), ≥24 weeks (168 days), ≥36 weeks (252 days), ≥48 weeks (336 days), etc.) will be provided.

For the interim analyses, the duration of exposure (days) for the continuation participants will be calculated as:

Duration of exposure (days) = the day of cut-off – the day of first dose of study treatment + 1.

For the interim analyses, the duration of exposure (days) for the discontinuation participants will be calculated as:

Duration of exposure (days) = the day of the last study visit – the day of first dose of study treatment + 1.

For the final analysis, the duration of exposure (days) will be calculated as:

Duration of exposure (days) = the day of the last study visit – the day of first dose of study treatment + 1.

The total exposure in patient years will be calculated as the total patient days divided by 365.25.

## **2.4.2 Prior, concomitant and post therapies**

The number and percentage of participants taking prior medication, concomitant medication will be summarized in separate tables by preferred term and Anatomical Therapeutic Classification (ATC) class for the Safety set. Corticosteroids will be summarized separately from other medications. For concomitant medication, the above summary will be performed using the data up to Week 28/Week 48 visit in addition to all available data at the time point for the analyses.

Prior medications will be defined as treatments taken and stopped prior to first dose of study treatment. Any medications given at least once between the day of first dose of study treatment and the day of the last study visit will be concomitant medications, including those which were started pre-baseline and continued into the treatment period.

In addition, the number and percentage of participants using non-drug therapies and procedures prior to and after the first dose of study treatment will be summarized by primary system organ class and preferred term. For non-drug therapies and procedures after the first dose of study treatment, the above summary will be performed using the data up to Week 28/Week 48 visit in addition to all available data at the time point for the analyses.

## **2.5 Analysis of the primary objective**

### **2.5.1 Primary endpoint**

The primary clinical question of interest is: What is the benefit of Canakinumab in achieving clinical improvement for Japanese AOSD participants without increased use of corticosteroids regardless of study treatment discontinuations for any reason?

The justification for the primary estimand is that it will capture the actual effect of canakinumab in the condition that participants use stable dose of corticosteroids.

The primary estimand is described by the following attributes:

1. Population: Japanese AOSD participants.
2. Endpoint: Adapted ACR 30 response at Week 8
3. Treatment of interest: canakinumab 4 mg/kg s.c. (maximum of 300 mg) with stable dose of corticosteroids.

Handling of remaining intercurrent events:

1. Systemic corticosteroid dose increase and/or iv corticosteroid use before Week 8 (i.e. between baseline and Week 8 visit) for any reason: consider as non-response (Composite variable strategy)
2. Study treatment discontinuation for any reason: ignore (if adapted ACR 30 at Week 8 is available, it will be included in the analysis) (Treatment policy strategy)

The summary measure: Proportion of participants who achieve adapted ACR 30 at Week 8

The primary efficacy analysis will be based on the data up to the time when the first 11 participants in the FAS have reached Week 28 (or prematurely discontinued prior to Week 28).

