6.2.2 Prohibited medication

Use of the treatments displayed in [Table 6-3](#) are not allowed after the start of study treatment.

Table 6-3 Prohibited medication

Medication	Prohibition period	Action taken
Anakinra	during treatment period	Discontinue study treatment
Tocilizumab, abatacept, rilonacept, rituximab and any other biologics (investigational or marketed)	during treatment period	Discontinue study treatment
Etanercept, adalimumab, infliximab, or any TNF inhibitor (investigational or marketed)	during treatment period	Discontinue study treatment
Oral JAK inhibitor	during treatment period	Discontinue study treatment
Leflunomide, thalidomide, cyclosporine, tacrolimus, or i.v. immunoglobulin (i.v. Ig)	during treatment period	Discontinue study treatment
6-Merceptopurine, azathioprine, cyclophosphamide, or chlorambucil	during treatment period	Discontinue study treatment
Dapsone or mycophenolate mofetil	during treatment period	Discontinue study treatment
Intra-articular, peri-articular or intramuscular corticosteroid injections	during treatment period	Discontinue study treatment
Any other investigational non-biological drugs	during treatment period	Discontinue study treatment
Live vaccination	during treatment period	Discontinue study treatment

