#### **2.5.2 Statistical hypothesis, model, and method of analysis**

The primary objective will be achieved if the null hypothesis is rejected at the 2.5% one-sided level of significance.

$H_0: p_{ACZ} \leq 0.40$  vs.  $H_A: p_{ACZ} > 0.40$ ,

with  $p_{ACZ}$  being the proportion of participants who achieved adapted ACR 30 at Week 8.

Frequency tables with the number and percentage of participants who achieved adapted ACR 30 response together with a 95% confidence interval will be provided based on the FAS. A binomial test using the normal approximation will be performed and the Wald asymptotic confidence interval with continuity correction will be presented. For hypothesis testing, one sided p-value will be presented.

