## **Discontinuation of study treatment before Week 8 for any reason**

Treatment policy strategy is applied to this intercurrent event. When a participant discontinued study treatment before Week 8, but adapted ACR 30 assessment at Week 8 is available, it will be included in the analysis.

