### **2.5.6 Supportive analyses**

The primary analysis will be repeated, using data from all 14 participants, based on the FAS at the timing of the Week 28 interim analysis. Hypothesis testing will not be performed.

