## **2.6 Analysis of the key secondary objective**

### **2.6.1 Key secondary endpoint**

The secondary clinical question of interest is: What is the effect of Canakinumab on oral corticosteroids tapering in Japanese AOSD participants after Week 8 up to Week 28?

The justification for the secondary estimand is that it will capture the ability of canakinumab on corticosteroid tapering based on the success criteria starting from Week 8 up to Week 28 after canakinumab administration.

The secondary estimand is described by the following attributes:

1. Population: Japanese AOSD participants who use systemic corticosteroid at baseline and are administered canakinumab at Week 8.

2. Endpoint: Successful oral corticosteroids tapering by Week 28. Participants will be considered as being able to taper oral corticosteroid according to pre-defined criteria depending on baseline dose.
3. Treatment of interest: canakinumab 4mg/kg.

The analysis will account for different intercurrent events as explained in the following:

1. Discontinuation of study treatment after Week 8 for any reason: If a participant early discontinued study treatment after Week 8 but had the Week 28 assessment regarding corticosteroid tapering, he/she will be included in the analysis.
2. Intravenous administration of steroid at any time between Week 8 and Week 28: If a participant had intravenous administration of steroid at any time between Week 8 and Week 28 assessment visit (i.e. between Week 8 visit and Week 28 visit), he/she will be considered as corticosteroid tapering failure at Week 28 regardless of whether the corticosteroid data is available (non-responder imputation)

The summary measure: proportion of participants who are able to taper oral corticosteroids successfully at Week 28.

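### The estimands do not separate use of another AOSD-active prohibited therapy from plain treatment discontinuation, so a post-switch response could count as a canakinumab success

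*SAP*

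**What the plan says.** **Prohibited therapy leads to discontinuation.** Protocol 6.2.2, Table 6-3, covers "Tocilizumab, abatacept, rilonacept, rituximab and any other biologics (investigational or marketed", TNF inhibitors, oral JAK inhibitors, several immunosuppressants, i.v. Ig, and intra-articular, peri-articular or intramuscular corticosteroid. The listed action is always to discontinue study treatment. Protocol 9.1.1 repeats prohibited treatment as a required reason for discontinuation.

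**Primary endpoint.** SAP 2.5.1 applies treatment policy: "Study treatment discontinuation for any reason: ignore (if adapted ACR 30 at Week 8 is available, it will be included in the analysis". SAP 2.5.3 repeats it: "When a participant discontinued study treatment before Week 8, but adapted ACR 30 assessment at Week 8 is available, it will be included in the" … The only event set to non-response is a systemic corticosteroid increase or iv corticosteroid before Week 8. A missing Week 8 assessment is non-response (SAP 2.5.4).

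**Key secondary endpoint.** SAP 2.6.1: "If a participant early discontinued study treatment after Week 8 but had the Week 28 assessment regarding corticosteroid tapering, he/she will be included". The only event set to failure is iv steroid between Week 8 and Week 28. SAP 2.6.3 carries the last available value forward when success cannot be derived; Protocol 12.5.1 limits this to missing body weight.

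**No other rule catches a switch.** SAP Table 5-1 excludes participants from the FAS only for missing consent or never being dosed. The supplementary estimand (SAP 2.5.5) only relaxes the corticosteroid rule. The supportive analysis (SAP 2.5.6) changes only the number of participants.

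**The concern.** The primary estimand is justified as capturing what canakinumab achieves while corticosteroids stay stable, and extra corticosteroid is accordingly a failure. Starting another active AOSD drug is a different event from simply stopping canakinumab, but the plan never names it. It falls into the category that is ignored, and whatever is then observed is used.

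In a randomised trial, a treatment-policy comparison would at least set switching in one arm against switching in the other. Here the observed proportion is compared with a fixed 40%, so benefit from the second drug cannot be told apart from benefit of canakinumab. No planned analysis would show how much of the result depends on such participants. With 11 participants in the confirmatory analysis, one classification can matter.

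**Working it through.** **Step 1. When could a post-switch response be counted?** The documents must supply an assessment made after the switch. There are three routes.

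- *Continued visits.* Protocol 9.1.1 contradicts itself. One sentence has all discontinuers complete an EOS visit and leave the trial. Another has them return for the scheduled follow-up visits, and the glossary and Protocol Section 8 agree with that. The stated minimum data for abbreviated visits are treatments and adverse events, with no ACR components.
- *Remapped EOS visit.* SAP Table 2-1 maps an EOS on Days 32-60 to Week 8 and on Days 173-200 to Week 28.
- *LOCF, key secondary only.* SAP 2.6.3 could supply a Week 28 result. It credits another drug only if the value carried forward was itself obtained after the switch.

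Without any of these, a switcher before Week 8 has a missing assessment and is a non-responder.

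**Step 2. Which endpoint is more exposed?** Protocol 9.1.1 mentions worsening at two consecutive visits after Week 4, but defines it as not meeting ACR 30 by Week 12, or non-response at two consecutive visits from Week 12. Discontinuation for non-response therefore falls mainly after the primary time point and inside the Week 8 to Week 28 window. The dose derivation (SAP 5.6.1) counts oral steroid only, so an intramuscular or intra-articular injection neither raises the derived dose nor triggers the iv-steroid failure rule.

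**Step 3. Weight of one participant.** Primary: 1/11 = 9.1 points. Key secondary, denominator at most 14: at least 1/14 = 7.1 points. The key secondary has no hypothesis test, so only the reported proportion is affected.

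**Step 4. The primary decision boundary.** The sample-size text is blacked out, so there is no planned power to reproduce. Inputs from SAP 2.5.1 and 2.5.2: null 0.40, one-sided 2.5%, n = 11 ("first 11 participants in the FAS have reached Week 28"), and "A binomial test using the normal approximation will be performed". Whether the test is continuity-corrected is not stated, so both forms are shown.

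SE under the null = sqrt(0.40 × 0.60 / 11) = 0.1477
z = (x/11 − 0.40) / SE; corrected z = (x/11 − 0.40 − 1/22) / SE

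| Responders | z | p, uncorrected | p, corrected | Wald 95% lower limit, corrected |
|---|---|---|---|---|
| 7/11 | 1.600 | 0.0548 | 0.0981 | 0.307 |
| 8/11 | 2.216 | 0.0134 | 0.0282 | 0.419 |

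Uncorrected, 8 responders are needed. Corrected, 8 fails and 9 are needed: (0.8182 − 0.40 − 0.0455)/0.1477 = 2.52, p = 0.006. Either way, recoding one responder at the boundary reverses the conclusion.

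**Step 5. Illustration of size.** Assume the uncorrected boundary of 8, that k of 11 switch, that each switcher is counted as a responder with probability q, and that everyone else responds at 0.40. Then

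P(at least 8) = Σ over j of C(k,j) q^j (1−q)^(k−j) × P(Bin(11−k, 0.40) ≥ 8−j).

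| k | Plan, q = 0.6 | Plan, q = 1.0 | Switchers set to non-response |
|---|---|---|---|
| 0 | 0.0293 | 0.0293 | 0.0293 |
| 1 | 0.0378 | 0.0548 | 0.0123 |
| 2 | 0.0484 | 0.0994 | 0.0038 |
| 3 | 0.0615 | 0.1737 | 0.0007 |

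Both k and q are assumptions; the documents give neither.

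**The case against.** The strongest reply is that the text closes most of the path for the primary. If discontinuers leave after an EOS visit, Week 8 is missing and counts as non-response, and only an EOS on Days 32-60 is remapped. An end-of-treatment visit is due as soon as possible (Protocol Section 8), leaving a new drug little time to act. Rescue medication is not allowed (Protocol 6.2.3), so a switch before Week 8 should be rare. This stands, and is why the reach in the primary is judged small. It does not remove the gap, because other protocol text keeps discontinuers in follow-up.

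A reader might infer that every switcher becomes a responder. The documents do not support that. The participant is assessed as observed and must still meet ACR 30, including no intermittent fever in the preceding week. Success in the key secondary also requires a dose reduction that meets the criteria, with ACR 30 maintained, and that endpoint covers only steroid users dosed at Week 8.

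A reader might also infer that the rule contradicts the stated treatment of interest. That goes too far. The clinical question explicitly accepts discontinuation for any reason, and the stable-dose wording concerns corticosteroids, which the composite rule enforces. The narrower point stands: starting another active drug is not the same event as discontinuation.

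Finally, intramuscular corticosteroid could be read as a systemic increase, and so as non-response in the primary already. That is a fair partial exception there. It does not carry over to the key secondary, whose rule names only intravenous steroid.

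**Conclusion.** The gap is real on the text. Use of an AOSD-active Table 6-3 therapy is absorbed into ignorable discontinuation in both estimands, and no composite event, FAS exclusion or supplementary analysis separates it. A post-switch response could count if an assessment exists.

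The practical reach is probably small for the primary and larger for the key secondary. The size is conditional: 9.1 points per participant at n = 11, at least 7.1 points in the key secondary, and one participant can decide the primary test at the boundary.

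It would be tempting to say that the primary result is inflated, or that a move from 7/11 to 8/11 settles it. The documents support neither: they give no switching rate, and that particular move crosses the threshold only if the test is uncorrected.

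**What to change.** 1. In SAP 2.5.1, 2.5.3 and 2.6.1, and Protocol 2.1 and 2.2, add an intercurrent event: use of a Table 6-3 medication with activity against AOSD, before Week 8 (primary) or between Week 8 and Week 28 (key secondary), is non-response under a composite strategy. Keep treatment policy for other discontinuations. List the medications that count, because Table 6-3 also contains live vaccination, and say how intramuscular steroid is classed.
2. The trial is open-label and the cut-off for the first 11 participants was 6Dec2022 (SAP 2.14). If the primary estimand cannot be changed after that date, prespecify the same rule as a supplementary analysis of both endpoints and report the number of participants affected.
3. Reconcile the conflicting follow-up sentences in Protocol 9.1.1, since they determine whether post-switch data exist.

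Cost: one sentence per estimand or one extra analysis per endpoint, using concomitant medication data already collected (Protocol 6.2.1, SAP 2.4.2). The response rate can only stay the same or fall, so the change cannot raise the type I error; in this small sample a fall could change the primary conclusion.

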### **Adapted ACR 30 criteria**

The adapted ACR 30 response derived by ePRO vender will be used in the analysis.

#### **2.5.2 Statistical hypothesis, model, and method of analysis**

The primary objective will be achieved if the null hypothesis is rejected at the 2.5% one-sided level of significance.

$H_0: p_{ACZ} \leq 0.40$  vs.  $H_A: p_{ACZ} > 0.40$ ,

with  $p_{ACZ}$  being the proportion of participants who achieved adapted ACR 30 at Week 8.

Frequency tables with the number and percentage of participants who achieved adapted ACR 30 response together with a 95% confidence interval will be provided based on the FAS. A binomial test using the normal approximation will be performed and the Wald asymptotic confidence interval with continuity correction will be presented. For hypothesis testing, one sided p-value will be presented.

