12.4.2 Statistical model, hypothesis, and method of analysis

The aim is to evaluate the treatment effect of canakinumab for Japanese AOSD participants on the adapted ACR 30 response at Week 8. The justification of the corresponding primary estimand are detailed in [Section 2.1](#).

The primary objective will be achieved if the null hypothesis is rejected at the 2.5% one-sided level of significance.

$H_0: p_{ACZ} \leq 0.40$ vs. $H_A: p_{ACZ} > 0.40$,

with p_{ACZ} being the proportion of participants who achieved adapted ACR 30 at Week 8.

Frequency tables with the number and percentage of participants who achieved adapted ACR 30 response together with a 95% confidence interval will be provided based on the FAS. A binomial test using the normal approximation will be performed and the Wald asymptotic confidence interval with continuity correction will be presented.

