### **2.5.4 Handling of missing values/censoring/discontinuations**

Missing adapted ACR 30 assessment at Week 8 will be imputed with non-responder regardless of the reason for missing data (non-responder imputation).

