### **Adapted ACR 30/50/70/90/100 response criteria**

The adapted ACR 30/50/70/90/100 at Week 8 and the adapted ACR 30/50/70/90/100 at each visit including Week 8 will be analyzed separately.

For the adapted ACR 50/70/90/100 at Week 8, the primary analysis will be repeated as performed for adapted ACR 30 except the statistical hypothesis testing. The results will be presented with the primary analysis of the adapted ACR 30. In addition, the adapted ACR 30/50/70/90/100 response at Week 8 will be summarized with the number and percentage of participants by the subgroups described in Section 2.2.1.

For the adapted ACR 30/50/70/90/100 at each visit, frequency tables with the number and percentage of participants achieving the adapted ACR 30/50/70/90/100 criteria will be provided by scheduled visit.

The line plot of the percentage of participants achieving the adapted ACR 30/50/70/90/100 response for each visit will be provided.

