## 2.14 Interim analysis

Two interim analyses will be performed after all participants have completed Week 28 to support the registration dossier, and Week 48 to supplement the dossier with long-term safety and efficacy data. At the interim analysis at Week 28, the primary efficacy analysis will be conducted based on the data up to the time when the first 11 participants have reached Week 28 (or prematurely discontinued prior to Week 28), that is 6Dec2022, CCI [REDACTED].

For the primary efficacy analysis with the first 11 participants, only the endpoints presented below will be analyzed.

- Participant demographics
- Baseline participant characteristics
- Adapted ACR 30/50/70/90/100 response at Week 8 (primary estimand)
- Subgroup analyses based on prior use of Tocilizumab
- Adapted ACR 30/50/70/90/100 response by visit

- Line plot of adapted ACR 30/50/70/90/100
- Successful oral corticosteroid tapering at Week 28
- Successful oral corticosteroid tapering by visit after Week 8
- Prednisone equivalent dose tapered to below 5 mg/day
- Oral corticosteroid dose (mg/day) by visit
- Each component of adapted ACR criteria by visit
- Rash by visit
- DAS28-CRP by visit
- DAS28-CRP response by visit
- EULAR response by visit
- Systemic feature score: Total score by visit
- Systemic feature score: Each component score by visit
- Ferritin level by visit
- Spaghetti plot of ferritin level by visit
- Number of tender/swollen joints
- Standardized CRP within normal range

The analysis set to be used in the analysis presented above will include up to about 11 participants.

After all participants have completed Week 28 and Week 48, two interim analyses will be performed on the efficacy and safety data during the study:

One will be at Week 28, to support the registration dossier and the other will be at Week 48 to supplement the dossier with long-term safety and efficacy data.

At the interim analyses, the data cut-off date for Week 28/Week 48 analysis will be the date of Week 28/Week 48 visit for the last participant. For efficacy analyses including PK/PD and biomarker-related analyses, the data up to Week 28/Week 48 visit for each individual participant will be included. For safety analyses and summaries for treatments, all available data will be included.

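### With 11 participants the primary test as worded has a true one-sided level of 2.93% rather than 2.5%, and the continuity-corrected Wald interval is unfit at high response rates

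*SAP*

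**What the plan says.** Protocol 12.4.2 and SAP 2.5.2 test H0: p ≤ 0.40 against p > 0.40 for adapted ACR 30 response at Week 8. The success criterion is: "The primary objective will be achieved if the null hypothesis is rejected at the 2.5% one-sided level of significance". The method, worded the same way in both documents, is: "A binomial test using the normal approximation will be performed and the Wald asymptotic confidence interval with continuity correction will be presented".

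The data set is small. SAP 2.5.1 bases the analysis on data up to the time when "the first 11 participants in the FAS have reached Week 28 (or prematurely discontinued prior to Week 28". SAP 2.14 hedges slightly: "The analysis set to be used in the analysis presented above will include up to about 11 participants". The denominator should stay at 11, because SAP 2.5.4 says: "Missing adapted ACR 30 assessment at Week 8 will be imputed with non-responder".

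The same interval carries over to other analyses. For adapted ACR 50/70/90/100 at Week 8, SAP 2.7.2 says that "the primary analysis will be repeated as performed for adapted ACR 30 except the statistical hypothesis testing". SAP 2.5.5 repeats the primary analysis for the supplementary estimand. SAP 2.5.6 adds: "The primary analysis will be repeated, using data from all 14 participants". Both of these exclude testing.

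Neither document specifies an exact test, an exact or score interval, or a rule for limits outside 0 to 100%.

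**The concern.** This is the only hypothesis test visible in the plan, and it decides whether the primary objective is met. With n=11 and p=0.40 only 4.4 responders are expected under the null, so a normal approximation may not hold its level. With so few possible outcomes, a small change in method can move the rejection threshold by a whole participant.

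The sentence is also incomplete. It names a continuity correction for the interval and is silent about the test. If that choice alters the threshold, the success rule is not fully specified.

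The interval raises a different problem. A Wald interval takes its width from the observed proportion, so it becomes too short when nearly everyone responds or nearly no one does. Such results are possible for ACR 30, and at either extreme for ACR 50 to 100. These intervals are meant for the registration dossier.

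**Working it through.** **Inputs.** n=11 (SAP 2.5.1), p0=0.40 and one-sided 2.5%, so critical z=1.960 (SAP 2.5.2; Protocol 12.4.2). Non-responder imputation keeps n at 11 (SAP 2.5.4). The sample-size text is redacted in the protocol and not visible in the SAP, so the intended power cannot be checked.

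**Formulas.**
- Test, no correction: z = (x/11 − 0.40)/√(0.24/11), with √(0.24/11) = 0.1477.
- Test, corrected: subtract 1/22 from the numerator.
- Exact p: P(X ≥ x) for X ~ Binomial(11, 0.40).
- Corrected Wald interval: p̂ ± [1.96·√(p̂(1−p̂)/11) + 1/22].

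| Result | z (p), no correction | z (p), corrected | Exact p | Corrected Wald 95% | Clopper-Pearson 95% |
|---|---|---|---|---|---|
| 7/11 | 1.600 (0.0548) | 1.292 (0.0981) | 0.0994 | 30.7 to 96.6% | 30.8 to 89.1% |
| 8/11 | 2.216 (0.0134) | 1.908 (0.0282) | 0.0293 | 41.9 to 103.6% | 39.0 to 94.0% |
| 9/11 | 2.831 (0.0023) | 2.523 (0.0058) | 0.0059 | 54.5 to 109.2% | 48.2 to 97.7% |
| 10/11 | 3.447 (0.0003) | 3.139 (0.0008) | 0.0007 | 69.4 to 112.4% | 58.7 to 99.8% |
| 11/11 | 4.062 (<0.0001) | 3.754 (0.0001) | <0.0001 | 95.5 to 104.5% | 71.5 to 100% |

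**Level of the test.** The stated 2.5% is not reproduced. Without correction the rule is 8/11 or more, and P(X ≥ 8) = 0.0234 + 0.0052 + 0.0007 + 0.00004 = 0.0293. The rule and level are the same if the sample variance is used in z, or if success means a corrected Wald lower limit above 40%. With a corrected test the rule is 9/11 or more, and P(X ≥ 9) = 0.0059. The exact binomial test gives that same rule.

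**Dependence on n.** The uncorrected test has exact level 2.50% at n=9, 1.23% at 10, 1.53% at 12, 3.21% at 13 and 1.75% at 14.

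**Weight on 8/11.** P(X = 8) is 26% at a true rate of 0.70 and 22% at 0.80.

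**Interval at the extremes.** At 11/11 the variance term is zero and only the ±1/22 (4.5 points) remains; the exact lower limit is 0.025^(1/11) = 71.5%. At 0/11 the interval is −4.5% to 4.5%, against an exact upper limit of 1 − 0.025^(1/11) = 28.5%. On all 14 participants, 14/14 gives 96.4% to 103.6% against an exact 76.8% to 100%.

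**Coverage of the corrected Wald interval.** This is the sum of binomial probabilities over every x from 0 to 11 whose interval contains the true rate:

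| True rate | 0.40 | 0.60 | 0.65 | 0.70 | 0.75 | 0.80 | 0.85 | 0.90 | 0.95 |
|---|---|---|---|---|---|---|---|---|---|
| Coverage | 94% | 94% | 93% | 96% | 95% | 90% | 83% | 68% | 43% |

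The same sum for Clopper-Pearson lies between 95.9% and 99.2% at these rates.

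**Power.** P(X ≥ 8) against P(X ≥ 9): 57% and 31% at a true rate of 0.70; 84% and 62% at 0.80.

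**The case against.** The excess is 0.43 percentage points, it arises at this sample size and one possible result, and the alternative overshoots in the other direction. The exact rule uses 0.59% of an allowed 2.5% and costs about 26 points of power at 0.70. The mid-p value at 8/11 is 0.0293 − 0.0234/2 = 0.0176, which is below 0.025. This stands: exact against approximate testing at n=11 is a trade-off, and the documents do not show that the normal test must be replaced.

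Timing also counts. SAP 2.14 dates the point at which the first 11 reached Week 28 as 6Dec2022, treatment is open-label (Protocol 6.5), and the current protocol and SAP are later. Changing the test now would change a stated success rule after those data existed. This stands too.

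Limits above 100% are raw formula values and might be cut at 100% for display, and success is judged by the test. But no truncation rule is given, and truncation would not mend the lower limit at 11/11 or the lost coverage. Coverage is close to nominal near a true rate of 0.70, so the fault is confined to high rates.

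A reader might infer three stronger things. One is that 8/11 is the expected result. The figure of at least 70% in Protocol 4.5 is for SJIA, for the paediatric criterion and at Day 15, so it supports only that 8/11 is plausible. Another is that the test should move to all 14 participants at no loss of power. The first-11 analysis follows regulatory feedback (Protocol 4.4), SAP 2.5.6 excludes testing on the 14, and at a true rate of 0.60 the exact test on 14 has 27.9% power against 29.6% for the present rule. The third is that only the Wald limit clears 40% at 8/11. The Wilson interval there is 43.4% to 90.3%, which also clears it.

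**Conclusion.** The concern holds in a limited form and should be fixed. On the plain reading that the test has no continuity correction, its true one-sided level at n=11 is 2.93%, not 2.5%. The consequence falls on exactly 8/11, which the plan would report as success at p=0.0134 although the exact p is 0.0293. If a corrected test was intended, the rule is 9/11 with level 0.59%. The documents do not settle which, and success at 8/11 turns on it.

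The finding on the interval does not depend on that reading. At n=11 the corrected Wald interval passes 100% at all four results that reject under the plain reading, nearly vanishes at 11/11, and undercovers clearly once the true rate is about 0.80 or more.

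The level rests on n being 11, which non-responder imputation supports, and on independent responses with a common rate. Nothing here shows that the primary conclusion will be wrong or that the method was chosen to favour a result: the documents contain no results, and the sample-size rationale cannot be seen.

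**What to change.** In SAP 2.5.2 and Protocol 12.4.2:

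- Replace the Wald interval with Clopper-Pearson for adapted ACR 30/50/70/90/100 and for the supplementary and supportive analyses. Do not pair a Wilson interval with an exact test, because the two would disagree at 8/11.
- State whether the test is continuity-corrected.
- If the uncorrected test is kept, state its true one-sided level as 2.9% and report the exact binomial p beside it. Say in advance how 8/11 will be described, since the test would reject while the Clopper-Pearson lower limit is 39.0%. It should not be presented as success at 2.5% without qualification.

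The cost is a few sentences and a change of analysis option, plus wider, somewhat conservative intervals.

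Replacing the test with the exact binomial (reject from 9/11) is an option rather than a requirement. It lowers the level to 0.59% and the power from 57% to 31% at 0.70 and from 84% to 62% at 0.80. Because it would follow the 6Dec2022 cut-off in an open-label trial, it would have to be recorded with its date and reason, for example in SAP section 4, which now lists no changes. The analysis should stay on the first 11 participants, with the 14-participant repeat left untested.
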